In addition to patients of MGH, subjects from the general greater Boston population will also be recruited. Subjects from the general population will be recruited through online advertisements run using the Galen Recruitment Service. Through this service, respondents will be filtered by qualifying questions. Contact information for qualified respondents will be provided to research study staff.

IV. Subject Enrollment

a.) Methods of enrollment

1. Patients may be approached by a research coordinator in the Neurointestinal Health clinic if they have a history of chronic constipation and agree to hear more about the trial
2. Patients may be called by the research coordinator prior to their appointment and asked if they would like to hear more about the trial
3. Any patients agreeing to hear more about the trial will learn more before beginning the informed consent process should they agree to participate as well as determining whether they meet all of the inclusion criteria
4. Patients may be contacted about the research study by their MGH physician on behalf of the research team. Afterward, patients may then be contacted by the research team directly.
5. Subjects who have provided their contact information through internet advertising may be contacted by the research team directly.

b.) Procedures for obtaining informed consent

1. Patients agreeing to participate will sign an informed consent with the study doctor at the time of enrollment, after proper informed consent has been provided by the site.

c.) Treatment assignment and randomization

1. Patients who have been enrolled and consented in the trial will be randomized with a ratio of 1:1:1 with 15 subjects per arm: 15 subjects on 3 capsules BID of CSP01, 15 subjects on 3 capsules BID (morning, evening) of carboxymethylcellulose (CMC), and 15 subjects on 3 capsules BID of placebo (sucrose).
2. We will stratify by Rome IV diagnosis of CIC vs. IBS-C to avoid clustering of IBS-C patients in one group.
3. The study personnel and patients will be blinded to treatment allocation.
4. Patients who fulfill study admission criteria and have a signed consent form will be assigned a 3-digit sequential patient number. The number will be used throughout the study.

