5. Randomization will be conducted via an interactive web-based response system (IWRS). Based on the randomized treatment assignment, an unblinded pharmacist at MGH will prepare the study treatment in a manner that ensures maintenance of the blind utilizing study-specific labels and completing details pertinent to the individual patient.
6. This is a double-blind study. The individual treatment assignment will not be revealed to patients or their representatives, study staff (except for the unblinded pharmacist), or the sponsor or the sponsor's representatives, until all patients complete the study and the database is locked. The unblinded pharmacist will maintain the treatment assignment for each patient.

V. Study Procedures

a.) Study visits and parameters to be measured

1. Eligibility Screen (Day -28 to -15)

- a. Vital signs, height, weight, and physical exam will be performed.
- b. Rome IV questionnaire to screen for CIC and IBS-C
- c. Blood sample collection (CBC, Chem 7, LFTs, Thyroid Hormone, ESR, and if applicable, serum pregnancy test)
- d. Urine sample for toxicity screening

2. Run-In Period (Day -14 to 0)

Day -14: After a screening visit in which patient eligibility will be determined through use of Rome IV constipation module along with other inclusion and exclusion criteria as above, there will be a two-week run-in period.

During this time no use of contraindicated medication per exclusion criteria or medications that may affect the bowel mobility will be allowed unless the subject has been on a stable dose for the last 3 months:

- a. Laxatives
- b. Prokinetic medications
- c. Anti-Depressant medications
- d. Medications for treatment of Parkinson disease
- e. Opiates
- f. Calcium-channel Blockers
- g. Aluminium/Magnesium
- h. Hydroxides
- i. Chronic use of non-steroidal anti-inflammatory drugs (NSAIDs) as defined by a frequency of at least 3 times a week for at least 6 months. Subjects on cardiac doses of aspirin may be enrolled in the study.

Day -7: Seven days into the run-in period, patients will undergo wireless motility capsule (WMC) testing to assess baseline motility. To allow for complete passing of the capsule, there will be a 7-day period following WMC ingestion prior to initiation of treatment to coincide with the end of the two-week run-in period.

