- e. Patients will be instructed to complete a simple, web-based daily diary using the Redcap system throughout the duration of the study which includes daily recording of number and time of bowel movements, complete/incomplete evacuation, and straining, abdominal discomfort, bloating, constipation severity, and overall relief using a nominal rating scale.
- f. **Day 1:** Subjects will begin taking study device. Patients will complete the Patient Assessment of Constipation Symptoms (PAC-SYM) and Quality of Life (PAC-QOL) to determine the severity of their constipation.
- g. **Day 15:** Following 14 days of treatment, patients will return to the clinic to undergo WMC testing to establish their motility profile on treatment and complete PAC-SYM, PAC-QOL questionnaires.
- h. **Day 22:** Following 21 days of treatment, patients will return to the clinic to return the WMC monitor and complete PAC-SYM, PAC-QOL questionnaires.
- i. **Day 31 (+3 days):** There will be a post-treatment period of 7 days during which time patients will continue to complete their daily diary. The clinical coordinator will call patients at the end of this follow-up period to ensure no adverse events occurred. After completion of the study, patients will be mailed the results of their SmartPill baseline test.

4. Schedule of Events

		Study						
		Run-in period			Treatment period			Post-treatment period
Time Point	Day -28 to -15	Day -14	Day -7	Day 0	Day 1	Day 15	Day 22	Day 31
Eligibility screen	X							
Informed consent	X							
Allocation				X				
CSP01 group				—————				
CMC group				◀	—————			▶
Placebo group				—————				
Rome IV questionnaire	X			X				
Daily diary		X	X	X	X	X	X	X
PAC-SYM		X		X	X	X	X	
PAC-QOL		X		X	X	X	X	
WMC testing			X			X		
Adverse events					X	X	X	X

5. There will be no routine monitoring of labs or imaging for the purposes of the study outside of usual care. Other study monitoring activities will be conducted as per Section IX of this protocol.
6. Patients enrolled in the study will not be allowed to be given standing laxative medications for prophylactic purposes, but rescue medications will be allowed on an as-needed (PRN) basis

b.) Investigational Product (IP) to be used

1. The IP will be supplied by the Sponsor and stored in the MGH inpatient pharmacy
 - a. CSP01 is supplied in capsule form (0.79 g per capsule, 2.37 g per dose)
 - b. CMC dose is supplied in capsule form (0.70 g per capsule, 2.1 g per dose)

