2. Specific data to be collected through patient-reported questionnaires
 - a. Spontaneous Bowel Movement (SBM) frequency rate
 - b. Complete Spontaneous Bowel Movement (CSBM) frequency rate
 - c. Stool consistency (Bristol Stool Form Scale)
 - d. Straining (Ease-of-Passage Scale)
 - e. Abdominal discomfort (Self Assessment on 0–10-point numerical rating scale)
 - f. Bloating (Self Assessment on 0–10-point numerical rating scale)
 - g. Constipation severity (Self Assessment on 0–10-point numerical rating scale)
 - h. Overall relief (Self Assessment on 0–10-point numerical rating scale)
 - i. Balloon Expulsion Time (BET) before and after
 - j. Constipation symptom severity (PAC-SYM)
 - k. Constipation quality of life (PAC-QOL)
 - l. Need for rescue laxatives
3. Study endpoints – As above
4. Statistical methods
 - a. Analysis populations
 - i. Intent-to-treat (ITT) population: all patients who are randomized will be included in the ITT population. This will be the primary population for all analyses of demographics, patient characteristics and disposition, and efficacy data.
 - ii. Safety population: All patients who are randomized and receive any study treatment will be included in the safety population. This will be the primary population for all analyses of safety data
 - iii. Per-Protocol (PP) population: All patients who are randomized and receive the study medication on each day of their hospitalization. Major protocol violations include the following:
 1. Prohibited concomitant medication usage (specifically standing laxatives during hospitalization)The PP population may be used for supplementary analysis of selected efficacy and safety data, as appropriate.
 - b. Endpoint analyses
 - i. Primary endpoint: Colonic transit times will be compared in a paired fashion for individual patients before and after the intervention by means of a repeated measures ANOVA using a 3x2 design to distinguish between the outcomes of the three different groups. We will also use multivariable linear regression to compare change in transit time after adjusting for confounders, specifically: presence of IBS-C, abnormal balloon expulsion testing indicating dyssynergic defecation ($BET \geq 2$ minutes), age, and sex.

ii. Secondary endpoints: The secondary endpoints will be compared in a similar fashion, with logistic regression adjusting for confounders.

c. Power analysis

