This is a randomized, double-blind, single-center clinical exploratory pilot comparing treatment with CSP01 to standard control (CMC) to placebo (sucrose) for prevention of constipation in patients with chronic idiopathic constipation. Notably, there is no data either from the wireless motility capsule or from radio-opaque marker transit studies establishing a clinically-meaningful threshold for change in transit time in response to any colonic motility agent, and our hope is that transit data combined with patient-reported outcomes (our secondary endpoints) from this pilot study would provide a meaningful transit improvement threshold that may be used in future research as well. There is some data demonstrating the effect of dietary fiber on colonic transit time.⁷ If we extrapolate data from the trial of dietary fiber on colonic transit time, which demonstrated a 10-hour difference in colonic transit time with a standard deviation of 12 hours, we would assume the same effect for our standard fiber (CMC) group. Assuming that CSP01 would give an additional 3-hour decrease in colonic transit over conventional fiber, our current sample size would have 94% (with $\geq 90\%$ considered excellent) power to detect a difference. Even with 30 total subjects, we would still have 80% power (see graph below which varies the sample size).

Power Analysis/Sample Size Determination.
For a Repeated Measures Anova with Indicated Specifications, & Assuming
A Test-Retest Correlation of 0.7

If we are more conservative with the effect of CSP01 over standard fiber and decrease the additional effect to 1 hour decreased colonic transit time (1/3 of what

we would expect), we would still have 88% power with our current sample size.

VII. Risks and discomforts

1. Device side effects and adverse events

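### Baseline colonic transit time is a covariate in neither planned model; adding it would cut the variance of a treatment contrast by about 13% at N = 45, given correlation 0.7 and equal SDs

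*Combined protocol and SAP*

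**What the plan says.** Section VI.4.b.i (Primary endpoint) names two analyses of CTT.

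- The first states: "Colonic transit times will be compared in a paired fashion for individual patients before and after the intervention", and this is to be done "by means of a repeated measures ANOVA using a 3x2 design to distinguish between the outcomes of the three different groups".
- The second is a multivariable linear regression on change in transit time, "adjusting for confounders, specifically: presence of IBS-C, abnormal balloon expulsion testing indicating dyssynergic defecation", and also for age and sex. Baseline CTT is not in that list, and no other section adds it.

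The baseline value is collected. In section V.a.2 (Run-In Period), at Day -7, "patients will undergo wireless motility capsule (WMC) testing to assess baseline motility". The second wireless motility capsule test is at Day 15 (section V.a.3.g): "patients will return to the clinic to undergo WMC testing to establish their motility profile on treatment".

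On randomization, section IV.c states: "We will stratify by Rome IV diagnosis of CIC vs. IBS-C". The power analysis (section VI.4.c) rests on a fiber trial that "demonstrated a 10-hour difference in colonic transit time with a standard deviation of 12 hours" and on "A Test-Retest Correlation of 0.7".

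**The concern.** In the repeated-measures ANOVA, baseline CTT is the first of two outcomes and not a covariate. With only two time points, the group-by-time test is identical to a one-way ANOVA on change. Subtracting baseline fixes its slope at 1, in that test and in the regression on change alike. The plan's own correlation of 0.7 implies a slope of 0.7 if the SDs are equal at the two visits.

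The difference matters through chance imbalance. With 15 patients per arm and SD 12 h, the standard error of a baseline difference between two arms is 4.4 h. A change score over-corrects by 1 - 0.7 = 0.3 of whatever difference arises: 1.3 h at one standard error and 2.6 h at two. The extra effect assumed for CSP01 over CMC is 3 h. This over-correction averages to zero over randomizations and is already reflected in the width of the planned confidence interval. It is therefore the source of the lost precision, not a bias and not a second harm. The pilot is also meant to inform a transit threshold for later research, so the precision of its estimates matters as well as its p-value.

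**Working it through.** **Inputs from the documents.** SD of CTT 12 h; test-retest correlation r = 0.7; CMC effect 10 h; CSP01 a further 3 h, or 1 h in the conservative case (all section VI.4.c). 15 per arm, 1:1:1 (section IV.c), so N = 45.

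**Assumptions.** Two-sided alpha 0.05; no change on placebo; SD 12 h at both visits and in every arm. The 13% figure does not depend on alpha.

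**1. Reproduce the plan's power.**
- Variance of change = 2 × 12² × (1 - 0.7) = 86.4, so SD 9.30 h.
- Mean changes 0, -10, -13 h have a sum of squares about their mean of 92.67. Noncentrality = 15 × 92.67 / 86.4 = 16.09. The noncentral F on 2 and 42 df gives 94.3% (plan: 94%).
- Mean changes 0, -10, -11 h give 88.2% (plan: 88%). With N = 30 and the 3 h case, the result is 79.8% (plan: 80%).
- Reading 12 h as the SD of change gives only 77.0%. The plan's figures therefore correspond to 12 h at each visit with r = 0.7.

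**2. Variance with baseline as a covariate.**
- Change score: 2(1 - r) = 0.60 SD².
- Baseline-adjusted: 1 - r² = 0.51 SD².
- Large-sample ratio: 0.51 / 0.60 = 0.85, a 15% cut.
- Cost of estimating the slope with three arms: 1 + 1/(45 - 3 - 2) = 1.025.
- Net ratio: 0.85 × 1.025 = 0.871, a 12.9% cut. A simulation of 100,000 trials gave 12.8%.
- 45 / 0.871 = 51.6, so 45 patients inform like about 52.

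**3. Consequences at r = 0.7 and SD 12 h at both visits.**

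| Quantity | Change score | Baseline-adjusted |
|---|---|---|
| Omnibus power, 3 h case | 94.3% | 96.8% |
| Omnibus power, 1 h case | 88.2% | 92.2% |
| Mean half-width of pairwise 95% CI (simulated) | 6.81 h | 6.36 h |
| Type I error (simulated, 30,000 trials) | 5.0% | 5.0% |
| CSP01 vs CMC power, 3 h | about 14% | about 15% |
| CSP01 vs CMC power, 1 h | 6.0% | 6.1% |

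**4. Range over the correlation (equal SDs).** The net ratio is [(1 + r)/2] × 1.025.

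| r | Net ratio | Omnibus power, 3 h case |
|---|---|---|
| 0.5 | 0.769 | 77% to 87% |
| 0.7 | 0.871 | 94.3% to 96.8% |
| 0.8 | 0.923 | 99% to above 99% |
| 0.9 | 0.974 | not computed |

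**5. Range over the baseline SD.** The documents give no separate baseline SD. Hold r = 0.7 and the follow-up SD at 12 h. The adjusted variance is then 144 × 0.51 × 1.025 = 75.3, whatever the baseline SD s. The change-score variance is 144 + s² - 2 × 0.7 × 12 × s.

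| Baseline SD s | Change-score variance | Ratio |
|---|---|---|
| 8.4 h | 73.4 | 1.025 |
| 10 h | 76.0 | 0.990 |
| 12 h | 86.4 | 0.871 |
| 15 h | 117.0 | 0.643 |

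**6. Chance imbalance.** 12 × √(2/15) = 4.38 h; 0.3 × 4.38 = 1.31 h, and twice that is 2.6 h.

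**7. The stratum term (simulated half-widths).** With no CIC/IBS-C difference, adding the stratum moves the baseline-adjusted half-width from 6.358 to 6.364 h. With an assumed 20 h difference and 5 of 15 IBS-C patients per arm, it falls from 6.56 to 6.37 h. The change score stays at 6.82 h either way, because a level difference between the strata cancels on subtraction.

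**The case against.** The planned analysis is not wrong. It compares change between randomized arms, holds its type I error, already uses baseline as one of the paired values, and belongs to an exploratory pilot. The headline power already exceeds the plan's 90% mark. The gain in the 1 h case concerns a three-arm omnibus test driven by active treatment against placebo, and the CSP01 versus CMC comparison hardly moves. All of this stands, and it limits the point to a suggested improvement.

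The size of the gain is also sensitive to an unknown. Entry criteria select on constipation, so the baseline spread could be narrower than the follow-up spread. At a baseline SD of 10 h with the correlation held at 0.7, the cut is only 1%, and at 8.4 h there is a small loss. This stands too, although holding the correlation fixed pushes the slope up to 1 at 8.4 h. If the slope stayed at 0.7, the net cut would be about 9% at 10 h and 6% at 8.4 h. The exposure is lopsided in favor of adjustment: at most about 3% lost, against 13% gained with equal SDs and about 36% at a baseline SD of 15 h.

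Finally, the case for a stratum term leans on an assumed CIC/IBS-C difference. That is fair. But the term costs almost nothing if there is no difference, and randomization used the stratum.

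**Conclusion.** The concern holds. Baseline CTT is measured in every patient by design, yet neither planned model uses it as a covariate. The cost is precision, not validity: about 13% of the variance of a treatment contrast at N = 45, which is worth roughly seven extra patients (52 against 45). This rests on the plan's correlation of 0.7 and on equal SDs of 12 h, an assumption under which the plan's own three power figures reproduce. The gain is larger at lower correlation or wider baseline spread, and close to nil if the baseline SD is about 10 h or less with the correlation unchanged. It does not make the trial able to separate CSP01 from CMC. It is worth considering because it is nearly free, not because the planned test misleads.

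**What to change.** In section VI.4.b.i, make the primary model a linear model for Day 15 CTT with treatment (three levels), baseline CTT and the CIC/IBS-C randomization stratum, and take the pairwise contrasts from it. Modeling change instead gives the same contrasts once baseline is a covariate. Add baseline CTT to the multivariable regression. Keep the 3x2 repeated-measures ANOVA as a sensitivity analysis. Settle the wording before unblinding.

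The cost is SAP text and two model degrees of freedom (baseline and stratum). No visit, test or patient is added, since both approaches need the same two capsule tests. If the baseline SD turns out near 0.7 times the follow-up SD, variance would be about 3% higher than with the change score.

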 - c. Matching placebo consists of an inert mixture supplied by the Sponsor in identical-appearing capsules
2. Rescue medications (in case of emergency)
 - a. If a subject experiences inadequate prevention of constipation while on the study treatment or placebo, the patient may be administered a rescue medication (laxative) at the discretion of the patient conferring with the Study physician or research NP consistent with “prn” orders or new orders from the medical team. Drugs that are available to treat constipation include: Colace (Docusate), Polyethylene glycol (Miralax), Senna (Senokot), magnesium citrate, and lactulose. Because constipation is not a side effect of the medication, all patients will be able to receive laxative doses as needed at their request throughout the study consistent with nurse’s or physician’s discretion without restriction.
 - b. Patients with no bowel movement for 5 consecutive days, who are in need of a rescue treatment, will be instructed to contact the investigator. The following treatment is recommended, as applicable, in the following order:
 - i. 1. Glycerin suppository
 - ii. 2. Enema
 - iii. 3. Laxadin/Bisacodyl tablets (3x5mg)
 - c. Administration of rescue treatment is at the discretion of the investigator based on an assessment of the subject; administration of rescue should be monitored and recorded.

c.) Data to be collected and timeline for collection

1. Primary endpoints
 - a. Colonic Transit Time (CTT)
2. Secondary endpoints
 - a. Spontaneous Bowel Movement (SBM) frequency rate
 - b. Complete Spontaneous Bowel Movement (CSBM) frequency rate
 - c. Stool consistency (Bristol Stool Form Scale)
 - d. Straining (Ease-of-Passage Scale)
 - e. Abdominal discomfort (Self Assessment on 0–10-point numerical rating scale)
 - f. Bloating (Self Assessment on 0–10-point numerical rating scale)
 - g. Constipation severity (Self Assessment on 0–10-point numerical rating scale)
 - h. Overall relief (Self Assessment on 0–10-point numerical rating scale)
 - i. Balloon Expulsion Time (BET) before and after
 - j. PAC-SYM change
 - k. PAC-QOL change
 - l. Need for rescue laxatives

c.) Adverse events

1. Definition of adverse events

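### Logistic regression is named as the adjusted model for all secondary endpoints, but 11 of the 12 are not binary and no responder cut-off is defined

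*Combined protocol and SAP*

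**What the plan says.** For the primary endpoint, colonic transit time (CTT), Section VI.4.b.i plans a 3x2 repeated measures ANOVA and then an adjusted model: "We will also use multivariable linear regression to compare change in transit time after adjusting for confounders". The covariates are IBS-C, age, sex and "abnormal balloon expulsion testing indicating dyssynergic defecation", the last defined as a balloon expulsion time (BET) of 2 minutes or more.

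For the secondary endpoints, Section VI.4.b.ii says only: "The secondary endpoints will be compared in a similar fashion, with logistic regression adjusting for confounders". The reference back to the primary analysis carries over the repeated measures ANOVA. The adjusted model changes from linear to logistic, and no reason is given.

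The 12 secondary endpoints are listed in Section V.c.2 and repeated, with slightly different labels, in Section VI.2. They include "Complete Spontaneous Bowel Movement (CSBM) frequency rate", "Balloon Expulsion Time (BET) before and after", "PAC-SYM change" and "Need for rescue laxatives".

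**The concern.** Binary logistic regression needs a yes/no outcome. If most of the endpoints are rates, scores or times and no rule turns them into responses, the stated model cannot be fitted to them as they are defined. Someone would have to choose a cut-off for each endpoint later, possibly with the data in view. Each cut would also discard information that the linear model planned for CTT keeps, in a trial with 15 patients per arm. If logistic regression was meant only where an outcome is binary, the sentence does not say so, and the adjusted model for the other endpoints is then unnamed. Either way the sentence does not settle the analysis.

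**Working it through.** **1. Classify the endpoints** (Section V.c.2, items a to l).

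| Type | Endpoints | Number |
|---|---|---|
| Rate | SBM, CSBM | 2 |
| Scale or rating | Stool form, straining, abdominal discomfort, bloating, constipation severity, overall relief | 6 |
| Time | BET | 1 |
| Score change | PAC-SYM, PAC-QOL | 2 |
| Yes/no | Need for rescue laxatives | 1 |

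Not binary: 2 + 6 + 1 + 2 = 11 of 12. Rescue use counts as binary only if it is read as any use, which the plan does not state.

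**2. Look for a cut-off.** Two thresholds come close. The limits of fewer than 3 CSBMs and at most 6 SBMs per week (Section III, inclusion criterion 5) are run-in eligibility rules. BET of 2 minutes or more (Section VI.4.b.i) defines a covariate. Neither defines a response, so the number of responder cut-offs is 0.

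**3. Information lost by a cut.** For a normal outcome and small effects, a cut at percentile p keeps the fraction φ(z_p)² / [p(1 − p)], where φ is the standard normal density.

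- Median: 0.3989² / 0.25 = 0.637. Of 45 patients: 45 × 0.637 = 28.6.
- Quartile: 0.3178² / 0.1875 = 0.539. Of 45 patients: 45 × 0.539 = 24.2.

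The median is the best case for a single cut.

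**4. Model size.** Two arm terms plus four covariates make six terms. With 45 patients, a median split leaves 22 in the smaller category, or 22/6 = 3.7 events per term. A quartile cut leaves 11, or 11/6 = 1.8.

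**5. Power, for illustration only.** The plan gives no effect size or power for any secondary endpoint, so there is no figure to reproduce. Take two arms of 15, a two-sided 5% test, no covariates and normal approximations, with d the assumed difference in SDs.

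- Continuous outcome: Φ(d√(15/2) − 1.96).
- Split midway between the arm means: compare proportions Φ(−d/2) and Φ(d/2).

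| Assumed d | Continuous | Split |
|---|---|---|
| 0.5 | 28% | 19% |
| 0.8 | 59% | 39% |
| 1.0 | 78% | 56% |
| 1.2 | 91% | 72% |

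The loss varies with the assumed effect. Borrowing the CTT assumptions of Section VI.4.c, CSP01 against placebo is 13/12 = 1.08 SD. On the change scale, with the plan's correlation of 0.7, it is 1.08/√(2 × 0.3) = 1.40 SD. In simulations of the six-term models with three arms of 15, assumed covariate prevalences and critical values calibrated to 5%, power was 78–81% (linear) against 58–59% (median-split logistic) on the first scale, and about 95% against 79% on the second. Which scale applies to a given secondary endpoint is not known.

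**The case against.** The strongest reply is that the information loss arises on one reading only. No section plans to dichotomise anything. The sentence could mean that the CTT approach carries over, with logistic regression where an outcome is binary, or that ordinal logistic regression is used for the scales. On those readings the losses in steps 3 and 5 do not arise. This stands as a limit on the size of the harm. It does not rescue the sentence, which covers the secondary endpoints without restriction and names neither alternative. Ordinal logistic regression would naturally suit six of the 11 endpoints and would leave the rates, BET and the PAC score changes without a natural model.

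It is also fair to say that this is an exploratory pilot and that only the adjusted analysis is unclear. That stands and lowers the priority.

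Three stronger inferences are not supported:

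- **A fixed loss of power.** A reader might infer that the trial loses some 15 to 20 percentage points of power on its secondary endpoints. That requires every endpoint to be dichotomised and effects to be borrowed from CTT.
- **Failure of the transit-threshold aim.** Section VI.4.c hopes to relate transit data to patient-reported outcomes. That is an association between endpoints and does not rest on this adjusted comparison of arms. The raw scores remain available whichever model is used.
- **Categorical ratings.** The diary text in Section V.a.3.e refers to "abdominal discomfort, bloating, constipation severity, and overall relief using a nominal rating scale", from which a reader might infer unordered categories. Sections V.c.2 and VI.2 both give 0–10 numerical scales, so this is probably a slip and is a separate clarification.

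**Conclusion.** The point holds. As written, the adjusted model does not fit 11 of the 12 secondary endpoints, and there is no cut-off that would make it fit. The count and the absence of cut-offs come directly from the text and rest on no assumption, apart from reading rescue use as any use; if it were a count, all 12 would be non-binary. The figures of at most 64% and 54% of the information kept apply if the sentence is read as binary logistic regression, and they assume a normal outcome and small effects. Any power comparison is illustrative, because the plan states no secondary effect size.

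The reach is limited: the CTT analysis and the unadjusted repeated measures ANOVA of the quantitative secondary endpoints are untouched. For an exploratory pilot this is a correction that should be made, at the low end of that grade.

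**What to change.** Replace the sentence in Section VI.4.b.ii with:

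> Quantitative secondary endpoints (SBM and CSBM rates; mean stool form, straining, abdominal discomfort, bloating and constipation severity scores; BET; PAC-SYM; PAC-QOL) will be compared by repeated measures ANOVA as for CTT, with adjusted analysis of change by multivariable linear regression using the covariates planned for CTT. When BET is the outcome, baseline BET replaces the abnormal-BET covariate. Overall relief will be compared between arms on its on-treatment mean score by linear regression with the same covariates. Need for rescue laxatives (any use during treatment, yes/no) will be compared as a proportion. Logistic regression will be used for this endpoint only, with a penalised (Firth) fit because events per model term will be few.

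Overall relief is handled on treatment only because relief before treatment has doubtful meaning. The penalised fit is needed because rescue use faces the same limit of at most 22/6 = 3.7 events per term with six terms. A count model for the rates, or a proportional-odds model for the scales, is equally acceptable if named before unblinding.

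The cost is small: analysis wording only, with no data beyond the endpoints and the BET covariate that the plan already names. The diary windows, the PAC baseline visit, the source of the BET values and the diary's description of the rating scale are separate clarifications and are not part of this point.
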